### **Adequacy of Protection against Risks**

**Informed Consent and Assent.** After a potential study participant is identified, a member of the study will see the parents and/or mother in the baby's room and explain the study. The risks and benefits will be discussed with the parents and time will be given to them to ask questions. It will be made known to them that no treatment will be withheld from their child if they participate in the study. The research team will attempt to obtain written consent after giving the parents a minimum of 24 hours to think about the study information and ask questions. Randomization will define study group assignment.

**Protection against Risks.** Our team will make every effort to protect all participants' confidential and private information in order to minimize possible study-associated risks. All findings related to any research will be available and provided to study participants in accordance with standard practices. We will also inform all participants that their participation is voluntary, and we will utilize study identification codes in place of personal identifiers on study materials. We will also employ storage and encryption techniques. All study personnel are required to renew Human

Subjects training biannually. No data will be accepted from or distributed to investigator or study staff if regulatory training is not current.

Vulnerable Subjects. This study population has been selected based on the frequency of postnatal growth problems observed in extremely preterm infants and the increased risk of adverse health outcomes in this vulnerable population. Because the probability of complications with protein-enriched human milk diets is not greater than the probability of complications with standard human milk diets, the category of children's risk level is 1 – research not involving greater than minimal risk. The risks of harm anticipated in the proposed research are not greater than those ordinarily encountered during the assessment of feeding tolerance.

### **Potential Benefits of the Proposed Research to Research Participants and Others**

Potential benefits of this study include safety and efficacy data on early life protein-enriched human milk diets as a dietary intervention to prevent nutritional deficits, reduce postnatal growth failure, and increase fat-free mass accretion in preterm infants. Better quantitative and qualitative outcomes of growth may also be associated with improved long-term neurodevelopmental outcomes.

Reductions of postnatal growth failure and improved nutritional parameters could improve long-term neurodevelopmental outcomes of infants who survive to hospital discharge. There will be benefit to the medical community in providing additional information on infant body composition of preterm infants.

### **Importance of the Knowledge to be Gained**

As the risk to individual participants is small and potential benefits are significant, the risk/benefit ratio is favorable. New knowledge on the effects of early diets on growth and the gut microbiome could measurably alter shift current practices and improve nutrition of preterm infants.

## **SECTION 4. ANALYTICAL PLAN**

---

### **4.1. STATISTICAL ANALYSIS PLAN**

All statistical analyses will use two-tail alpha to reject null hypotheses at 0.05, using R software. Continuous variables will be summarized as means  $\pm$  standard deviations (SD) or as medians and interquartile ranges (IQRs). Categorical variable will be summarized as frequencies and proportions. Group differences will be evaluated using the T Test or Wilcoxon test for continuous variables and chi-square for categorical variables. The effect size of the primary outcome will be expressed as the mean difference with 95% confidence intervals (CIs). Risk ratios (RRs) with 95% CIs will be reported for categorical outcomes. All of the efficacy and safety outcomes of the trial will be analyzed with the intention-to-treat principle.

To analyze our longitudinal microbiome data, we will use either negative binomial models or zero-inflated models. Since there is no explicit formula to calculate power and detect taxa based differences on neither negative binomial nor zero-inflated models, we performed extensive simulation studies to assess the statistical power needed to identify significant taxa with the proposed trial. We employed the function sim in the R package NBZIMM (<https://github.com/nyiuab/NBZIMM>) to simulate longitudinal microbiome count data, and then used negative binomial mixed models to analyze the simulated counts. For the proposed longitudinal microbiome study design (i.e. with 75 infants in the intervention group and 75 infants in the control group that will have 3 to 6 stool samples collected over time), we will achieve  $\sim$ 80% power to detect  $\sim$  2-fold effects. Since there is no explicit formula for analytically calculating power for detecting taxa based on neither negative binomial nor zero-inflated models, we performed extensive simulation studies to assess the statistical power to identify significant taxa with the proposed study design. We employed the function sim in the R package NBZIMM (<https://github.com/nyiuab/NBZIMM>) to simulate longitudinal microbiome count data, and then used negative binomial mixed models to analyze the simulated counts. To minimize possible bias and yield reasonable count values that are similar to real longitudinal microbiome data, we randomly generated the parameters (including the fixed fold-change effect, random effect, dispersion parameter, zero-inflation probability, etc.) in the model from reasonable ranges. For the proposed longitudinal microbiome study design (i.e. with 75 infants in the intervention group and 75 infants in the control group that will have 3 to 6 stool samples collected over time), we will achieve  $\sim$ 80% power to detect  $\sim$  2-fold effects under a significance level of 5%.

For clinical and microbiome outcomes, adjusted analyses will be performed with the following covariates: volume intake in ml/kg, proportion of human milk intake, exposure to antibiotics after birth (i.e., number of days receiving antibiotics), race, sex, gestational age, and maternal use of antibiotics.

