#### **3.2.2. Consent Procedures**

Written informed consent will be obtained by the first 96 hours after birth to allow treatment allocation before or on the first day of enteral feeding. If a potential participant is identified, a member of the study will see the parents and/or mother in her room or the baby's room and explain the study. The risks and benefits will be discussed with the parents and time will be given to them to ask questions. It will be made known to them that no treatment will be withheld from their infant if they participate in the study. Randomization will define study group assignment.

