### 3.2.5. Blinding/Masking

Caregivers and primary outcome evaluators will be masked. Nutrition room staff not involved in patient care will be responsible for determining participant allocation to one of the supplementation groups by opening sequentially numbered sealed envelopes, dispensing feeding syringes with the allocated human milk diet (protein-enriched or usual), and masking caregivers administering the assigned dietary intervention.

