### 3.2.6. Control or Monitoring of Co-interventions

This pragmatic trial will compare protein-enriched and usual human milk diets under normal clinical circumstances with no effort to strictly control interventions other than dietary intervention. Therefore, clinical care will be conducted at the clinician's discretion.

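### Fat-free-mass Z-score is compared unadjusted, and the only adjusted covariate list mixes baseline with post-allocation variables and omits birth size; a baseline-only model should be pre-specified

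*Combined protocol and SAP*

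**What the plan says.** The combined protocol and SAP describes two kinds of analysis for clinical outcomes, both in section 4.1.

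- **Unadjusted comparison.** "Group differences will be evaluated using the T Test or Wilcoxon test for continuous variables and chi-square for categorical variables". The primary effect is to be reported as a mean difference with a 95% confidence interval, and no covariate is attached to it. Section 4.2 bases the sample size on a two-sample t-test. No analysis is labelled primary, but the two sections together imply that this one is.
- **Adjusted analyses.** For clinical and microbiome outcomes alike, "adjusted analyses will be performed with the following covariates: volume intake in ml/kg, proportion of human milk intake, exposure to antibiotics after birth" (counted in days), followed by "race, sex, gestational age, and maternal use of antibiotics". The model form is not given. Nor does the text say whether all seven terms enter one model, or how these analyses rank against the unadjusted one. No measure of size at birth is listed, and no model restricted to baseline variables is defined.

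The stated aim is intention to treat: "All of the efficacy and safety outcomes of the trial will be analyzed with the intention-to-treat principle".

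Three other passages bear on how to read the list. Consent is timed "to allow treatment allocation before or on the first day of enteral feeding" (section 3.2.2). Section 3.2.5 states: "Caregivers and primary outcome evaluators will be masked". Section 3.2.6 leaves co-interventions open: "clinical care will be conducted at the clinician's discretion".

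**The concern.** There are two linked issues.

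**The adjusted analysis.** Three of the seven covariates are not baseline variables. If the assigned diet changes feeding tolerance, feed interruptions or infection, it can change feed volume, human-milk proportion and antibiotic days. Conditioning on those variables can then remove part of the diet's effect. It can also introduce bias through causes they share with the outcome. The fitted treatment coefficient need not be the total effect of assignment. Because the plan gives the adjusted analyses no stated role, a reader faced with two different estimates could not tell which answers the trial's question.

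**The unadjusted analysis.** It is valid, and nothing in the covariate list biases it. It may give up precision that baseline variables could supply without extra patients. The choice between t-test and Wilcoxon for the primary outcome is also left open; one named linear model would settle it.

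**Working it through.** **1. Timing of each covariate relative to allocation**

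| Covariate (section 4.1) | Timing |
|---|---|
| Race, sex, gestational age | Baseline |
| Maternal antibiotics | Baseline, if use before delivery is meant |
| Feed volume (ml/kg) | At or after allocation, since allocation is before or on the first feeding day (3.2.2) |
| Human-milk proportion | At or after allocation, for the same reason |
| Antibiotic days after birth | Counted from birth; may partly precede allocation (consent can run to 96 hours), otherwise after it |
| Birth weight or other birth size | Not listed |

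**2. The plan's own sample size**

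Inputs from section 4.2: difference 0.5, SD 1, 80% power. Section 4.1 gives two-sided alpha 0.05.

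n per arm = 2 × (1.960 + 0.842)² × 1² / 0.5² ≈ 62.8, so 63 per arm and 126 in total. This matches the stated 126.

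**3. Unadjusted power and precision at 63 per arm**

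SE = √(2/63) = 0.178. Noncentrality = 0.5/0.178 = 2.806, with 124 df. Noncentral-t power is 79.5%. The 95% CI half-width is 1.979 × 0.178 = 0.353 Z.

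**4. Baseline-adjusted power**

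Let R² be the share of outcome variance explained by the baseline covariates. The documents do not give it, so every value below is an assumption. Ignoring the cost of fitting covariates, the standardised effect is 0.5/√(1 − R²). To count that cost for three covariates, df = N − 5, and the variance of the treatment estimate is multiplied by (N − 3)/(N − 6) for chance imbalance. With N = 126 the factor is 123/120 = 1.025.

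Example at R² = 0.10: SE = √(2/63 × 0.90 × 1.025) = 0.171, noncentrality 0.5/0.171 = 2.92, df 121, power 82.6%, half-width 1.980 × 0.171 = 0.339 Z.

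| R² (assumed) | Power, cost ignored | Power, three covariates | Half-width, three covariates |
|---|---|---|---|
| 0 | 79.5% | 78.5% | 0.357 |
| 0.05 | 81.5% | 80.5% | 0.348 |
| 0.10 | 83.5% | 82.6% | 0.339 |
| 0.20 | 87.6% | 86.7% | 0.319 |

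Adjustment breaks even with the t-test at R² of about 0.025. Below that it loses up to about 1 point. At R² of 0.05, 0.10 and 0.20 it gains about 1, 3 and 7 points.

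**5. Sensitivity to the evaluable number**

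With the stated 20% loss from 75 per arm, 75 × 0.80 = 60 remain. Unadjusted power is then 77.5%. Three-covariate power is 76.4, 78.5, 80.7 and 85.0% at the same four R² values, with break-even at about 0.026. The gap between 63 and 60 per arm is a separate sample-size matter and is not argued here.

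**6. Simulation check**

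20,000 replicates at 63 per arm, with three independent baseline covariates sharing R² equally, gave adjusted power of 78.7, 80.7, 82.8 and 86.8%, and t-test power of 79.2–79.8%. Type I error at R² of 0 and 0.10 was 4.8 and 5.1% for the t-test, and 4.9% at both for the adjusted model. Both analyses hold their level.

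**The case against.** The sentence on the t-test contains no error. Test, effect measure and sample-size basis agree with one another, so replacing the test could be called a design preference. The gain rests on an R² that the documents do not give, and it is small unless R² approaches 0.20. The outcome is already age-indexed and measured at a fixed 36 weeks postmenstrual age, which may leave gestational age little to explain. A birth-weight Z-score needs a reference standard, and none is named. The adjusted analyses are not called primary, masking limits how far the diet can alter care, and intake-adjusted models are legitimate as supplements. On this view, only a request to label them remains.

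Much of this stands. The unadjusted test is valid, the precision gain is uncertain, and any shift in the adjusted estimate is conditional and of unknown direction.

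It does not dispose of the point. The covariate list is expressly for clinical outcomes, it is the only adjustment described, and section 4.1 promises intention to treat for all efficacy and safety outcomes. Masking caregivers does not stop an infant's tolerance of the diet from affecting feeding or antibiotic use, and care is discretionary. Followed as written, the adjusted analysis need not estimate the promised effect. Correcting that changes the model as well as its label.

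**Conclusion.** The concern holds, as a change that should be made rather than a flaw that invalidates the trial. The implied primary comparison is sound. The adjusted analysis is not suited to estimating the total effect of assignment, because its single list includes feed volume, human-milk proportion and antibiotic days. The likely gain in precision from a baseline-only model lies between a loss of about 1 power point (R² = 0) and a gain of about 7 (R² = 0.20) at 63 per arm. That range rests on the plan's difference of 0.5 and SD of 1 and on assumed R² values. The sponsor may be able to estimate R² from the earlier feeding trial used for the sample size. No figure can be put on the shift in the adjusted estimate. Confidence is medium.

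**What to change.** Amend section 4.1, before any unblinded outcome data are seen, as follows:

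- Name as primary a linear model of FFM-for-age Z-score at 36 weeks postmenstrual age on treatment, gestational age, sex and birth-weight Z-score, stating the birth-weight reference used. Report the adjusted mean difference with its 95% CI.
- Keep the unadjusted t-test as a supportive analysis.
- Remove feed volume, human-milk proportion and antibiotic days from any model meant to estimate the effect of assignment. Label models that contain them exploratory.

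The cost is SAP wording and slight extra analysis, with no added patients or visits. Sex and gestational age are already in the list, and birth weight is implied by the growth-velocity outcome in section 3.2.8. The worst case is a loss of about 1 point of power if the three covariates explain nothing.

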### 3.2.4. Study Intervention and Comparison

Usual feeding practices in our neonatal unit include: 1) administration of enteral feeds as intermittent bolus gavage every 3 hours; 2) initiation of trophic feeds within the first 96 hours after birth with 20-25 ml/kg/d; 3) progression of enteral feeds with daily increments of 20-25 ml/kg/d usually before postnatal day 7; 4) use of donor human milk as an alternative to mother's own milk if the mother is not able to supply her own milk, and 5) addition of bovine-based products that increase protein content of human milk at approximately postnatal day 14 after full enteral nutrition is established ( $> 120$  ml/kg/d) [Figure 4].

Intervention group: Infants in the intervention group will receive expressed human milk or donor human milk on feeding day 1 (within the first 96 hours after birth). On feeding day 2, a human milk-based product that increases protein content (Prolact®, Prolacta Bioscience, Inc. City of Industry, CA) will be added to human milk. This practice will continue until standard bovine-based human milk fortifiers are ordered.

Control group: Infants in the control group will receive expressed human milk or donor human milk from feeding day 1. This practice will continue until standard bovine-based products are ordered.

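### The adjusted analyses condition on feeding volume and human milk proportion, which accrue essentially after allocation, and on antibiotic days, which may do so in part, so they need not estimate the effect of assigning the diet.

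*Combined protocol and SAP*

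**What the plan says.** All references are to the combined protocol and SAP.

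- **Covariates (4.1).** "adjusted analyses will be performed with the following covariates: volume intake in ml/kg, proportion of human milk intake, exposure to antibiotics after birth". The list continues with race, sex, gestational age and maternal antibiotic use. It applies to clinical and microbiome outcomes. No measurement window is given for any of the intake or antibiotic variables.
- **Allocation (3.2.2).** Consent is obtained within 96 hours of birth "to allow treatment allocation before or on the first day of enteral feeding".
- **Start of the diet contrast (3.2.4).** "On feeding day 2, a human milk-based product that increases protein content" is added to the milk in the intervention arm. Both arms receive human milk from feeding day 1.
- **Masking and co-interventions (3.2.5, 3.2.6).** "Caregivers and primary outcome evaluators will be masked". There is "no effort to strictly control interventions other than dietary intervention", and clinical care is left to the clinician.
- **Unadjusted analysis (4.1).** "Group differences will be evaluated using the T Test or Wilcoxon test for continuous variables and chi-square for categorical variables". The primary effect is a mean difference with a 95% confidence interval. "All of the efficacy and safety outcomes of the trial will be analyzed with the intention-to-treat principle".
- **Microbiome (4.1).** "To analyze our longitudinal microbiome data, we will use either negative binomial models or zero-inflated models". No covariates are listed at that point; the adjusted analyses follow in a later paragraph.

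The plan declares no mediation aim. It does not label the adjusted analyses as primary, secondary or sensitivity.

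**The concern.** Randomisation balances what is fixed before allocation. A variable measured later can itself be changed by the assigned diet. Conditioning on it then removes part of the diet's effect or, where the variable and the outcome share an unmeasured cause such as illness severity, brings in confounding that randomisation had excluded.

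The three covariates are not equally exposed:

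- **Volume intake** accrues essentially after allocation and could respond to feeding tolerance under the assigned diet.
- **Antibiotic days** are counted from birth. An infant treated only in the first days could have most of them before allocation; later courses would fall after it and could follow complications. Sepsis and necrotising enterocolitis are safety outcomes (3.2.9), so adjusting those comparisons for antibiotic days could partly adjust for the outcome itself. For the weekly stool samples (3.2.11), a total without a window can include days after the sample was taken.
- **Human milk proportion** also accrues after allocation, but the documents give no clear route by which the diet would change it.

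Maternal antibiotic use has no stated timing either. It is a baseline variable only if limited to use before allocation. This is a minor point.

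At stake are which microbiome result would be read as the main one, and how an adjusted clinical estimate would be read if it differed from the unadjusted one.

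**Working it through.** **1. The plan's own figure.** Section 4.2 uses a difference of 0.5 Z, SD 1, two-sided alpha 0.05 and 80% power. The normal approximation gives n = 2 × (1.960 + 0.842)² / 0.5² = 62.8, so 63 per group and 126 in total, as stated. (The exact t-test needs 64 per group.) The calculation involves no covariates, so the concern does not touch it.

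**2. Inputs for the illustration.** From 4.2: true difference 0.50 Z, SD 1, and 75 per group less 20%, which leaves 60. The documents give no effect of diet on the covariates, so two inputs are assumed:

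- a = shift of the covariate caused by allocation, in SD: 0, ±0.1, ±0.3
- b = slope of FFM Z-score on the covariate within arms: 0.3 or 0.5 Z per SD

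**3. FFM.** In a linear model, adjusted estimate = 0.50 − a × b.

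| a (SD) | b = 0.3 | b = 0.5 |
|---|---|---|
| 0 | 0.50 | 0.50 |
| +0.1 | 0.47 | 0.45 |
| −0.1 | 0.53 | 0.55 |
| +0.3 | 0.41 | 0.35 |
| −0.3 | 0.59 | 0.65 |

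Simulation with 60 per group and 4000 replicates agreed: for example, 0.349 for a = +0.3 and 0.650 for a = −0.3 at b = 0.5. The unadjusted estimate stayed at 0.49 to 0.51 throughout.

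The distortion is 0 to 0.15 Z. To move the estimate by 0.10 Z, the shift must be 0.10/0.3 = 0.33 SD or 0.10/0.5 = 0.20 SD. For scale, the unadjusted standard error is √(2/60) = 0.183, a 95% half-width of 1.96 × 0.183 = 0.36 Z.

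**4. No true effect, shared cause.** Let illness severity load 0.5 on both the covariate and FFM, so the induced slope is 0.5 × 0.5 = 0.25. The adjusted estimate is −a × 0.25: 0 with no shift, −0.075 at a = +0.3 and +0.075 at a = −0.3 (simulated −0.003, −0.074 and +0.076).

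**5. A taxon with a true 2-fold effect.** In a log-linear count model, adjusted fold = 2 / f^a, where f is the fold change per SD of covariate (assumed 1.5 or 2).

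| a (SD) | f = 1.5 | f = 2 |
|---|---|---|
| 0 | 2.00 | 2.00 |
| +0.1 | 1.92 | 1.87 |
| −0.1 | 2.08 | 2.14 |
| +0.3 | 1.77 | 1.62 |
| −0.3 | 2.26 | 2.46 |

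This formula need not carry over to the zero-inflated models that 4.1 also allows.

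**The case against.** **The FFM comparison is safe.** The t-test, the mean difference and the sample size all point to the unadjusted analysis as the main one. This stands, although no sentence says so. For FFM the issue is how a supplementary model would be read.

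**No shift is shown.** Section 3.3 cites earlier high-protein studies, mainly in formula-fed infants, without tolerance problems, and expects complications to be no more likely on the enriched diet. Masking also weakens any route through knowledge of the arm. This stands as a reason not to presume bias. But these are expectations, they do not exclude fewer complications on the enriched diet, and the statement on feeding interruptions compares participants with non-participants, not the two arms. Masking does not block a route through the infant's own response.

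**Intention to treat is not breached.** Adding covariates neither moves nor drops infants. This stands: the problem is what the adjusted estimate measures.

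**The microbiome order is clear enough.** Count models come first and adjusted analyses after, so the unadjusted model is the natural reading. That is reasonable, but it remains an inference for an outcome that 3.2.7 names as primary.

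**The illustrated sizes are modest.** Even 0.15 Z is under half of 0.36 Z, and that half-width belongs to the unadjusted estimate. At b = 0.5 the adjusted half-width is about 0.36 × √(1 − 0.25) = 0.31. Chance alone also gives covariate differences with a standard error of 0.18 SD, so a gap between the two estimates would not prove this bias. Both remarks are right. They limit the severity and show why the reading should be settled in advance.

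**Conclusion.** The concern holds, as a point that should be fixed and does not threaten the main FFM comparison. Confidence is high on the timing of volume intake and human milk proportion, and on antibiotic days lacking a cut-off. Whether bias would occur is unknown, because it depends on a shift by arm that the documents neither show nor exclude. The case is weakest for human milk proportion. Every size above rests on assumed shifts and slopes and shows only what is possible. The practical gap is widest for the microbiome, where the model that carries the primary result is not identified.

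**What to change.** In 4.1:

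- Restrict the adjusted effect estimates to variables fixed before allocation: gestational age, sex, race, maternal antibiotics given before allocation and, if wanted, infant antibiotic days before allocation.
- State that the unadjusted FFM comparison, and a microbiome model without post-allocation covariates, are the main analyses.
- Report volume intake, human milk proportion and post-allocation antibiotic days by group, or use them only in an exploratory mediation analysis labelled as such.

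The cost is a few sentences, plus splitting antibiotic days at allocation. No further infants are needed, and the planned t-test keeps its power. The adjusted models may lose some precision. If the removed covariates explain 5% to 25% of FFM variance beyond the baseline ones (assumed), the standard error rises by a factor of 1/√(1 − R²), which is 1.026 to 1.155, or about 3% to 15%.
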